2. STUDY DESIGN

2.1. Summary of Study Design

This randomized withdrawal study (MVT-601-035) is an international phase 3 double-blind, placebo-controlled study that enrolled eligible patients with uterine fibroids who have completed the 24-week treatment period in a pivotal study (study MVT-601-3001 or study MVT 601-3002) and the 28-week treatment period of the LTE study, MVT-601-3003. When including treatment during a pivotal study and the extension study, patients completing this randomized withdrawal study will have received up to a total of 104 weeks of treatment with relugolix.

All consenting patients completing MVT-601-3003 with a response to treatment were eligible to participate. A responder was defined as a patient who demonstrated a menstrual blood loss of < 80 mL and at least a 50% reduction from a pivotal study baseline menstrual blood loss volume on the alkaline hematin analysis of the FPs returned at Week 48 in MVT-601-3003. The objectives of the current study are to evaluate long-term efficacy and safety of treatment with relugolix + E2/NETA for up to 104 weeks (total treatment duration includes the pivotal study, the extension study, and the randomized withdrawal study). Approximately 360 patients completing the extension study and meeting the definition of a responder as well as all other eligibility criteria were expected to be randomized 1:1 to blinded treatment with oral relugolix + E2/NETA or placebo, once daily, for up to 52 weeks. For patients whose menstrual bleeding returned to ≥ 80 mL (heavy menstrual bleeding), treatment with open-label relugolix + E2/NETA was to be restarted.

Screening procedures were to be done on the same day as the Week 52 visit for MVT-601-3003. This visit will be referred to as the “Week 52/Baseline visit”.

Patients were to receive the last dose of study drug in the study MVT-601-3003 on the day of the Week 52/Baseline visit (per the LTE study protocol) and to be dispensed study drug for this randomized withdrawal study in the clinic after being determined eligible for this study and providing informed consent to participate. The first dose of study drug for the randomized withdrawal study was to be self-administered the next morning following the Week 52/Baseline visit. Dosing was to be confirmed by telephone.

Patients were to be asked to collect FPs for alkaline hematin analysis and to return them at each visit until the analysis confirmed the return of heavy menstrual bleeding (defined as menstrual blood loss volume of ≥ 80 mL). The patients were then to be offered re-treatment with open-label relugolix +E2/NETA with the onset of the next menses. They were to continue collection of FPs for alkaline hematin analysis until two consecutive analyses confirmed resolution of heavy menstrual bleeding (menstrual blood loss of < 80 mL). Patients who experienced a return of heavy menstrual bleeding (or terminate early because they have a return of heavy menstrual bleeding) but who decline retreatment with open-label study drug were to complete an Early Termination visit and a 30-day Safety Follow-Up visit.

At the Week 104/Early Termination visit, all other patients were to have an assessment of bone mineral density (BMD) via dual-energy x-ray absorptiometry (DXA). Patients were to complete the bleeding diary daily, including compliance with study drug, vaginal bleeding, and use of FPs.

If a patient enrolls directly into another relugolix clinical study upon completion of the Week 104/Early Termination visit, then the Safety Follow-Up visit and the follow-up procedures performed under this protocol may be waived.

2.2. Sample Size Considerations

Because this is an extension of study MVT-601-3003, the sample size of this study was based on approximately the number of patients who completed a pivotal study (n = 780 patients in total), and who participated in the LTE study (n = 600 patients in total assuming about 20% dropout rate at 6 months from the pivotal studies). Assuming the proportion of responders at Week 52 in MVT-601-3003 LTE study is 60%, it was estimated that approximately 360 patients were to be randomized into this study.

With 360 patients, the study would have at least 90% power to detect a difference of 20% or greater between relugolix+ E2/NETA group and placebo group for the primary endpoint. The following assumptions were used to determine the sample size for this study:

- 2-sided type I error rate: 0.05
- Randomization: 1:1
- Responder rate for placebo group: 40%
- Responder rate for relugolix + E2/NETA group: 60%
- Dropout rate: 20%

3. PLANNED ANALYSES

3.1. Interim Analyses

There are no planned interim efficacy analyses.

3.2. Final Analyses

The final analysis of efficacy and safety data will occur after approximately 360 patients (projected to be responders from MVT-601-3003) who have been randomized and have had the opportunity to complete the study through either the Week 104 visit or the 30-day Safety Follow-up visit.

3.3. Safety Follow-Up Analyses

Patients who experience a BMD loss of $\geq 7\%$ from the pivotal study baseline at any of the anatomical sites assessed will be discontinued from the study and will undergo another bone densitometry scan as described below. Patients with a BMD loss of $\geq 7\%$ at lumbar spine, total hip, or femoral neck at their Week 104/Early Termination visit relative to pivotal study baseline measurement will undergo another bone densitometry scan at 6 (± 1) months after the last dose of study drug and will be contacted to obtain information about medications and conditions (eg, pregnancy) that might affect BMD through the time of the follow-up bone densitometry scan. Patients should be assessed for secondary causes of bone loss and followed-up further if the 6-month follow-up scan does not show improvement, unless an alternative etiology has been identified. The follow-up bone densitometry scan will be submitted for central reading.

Patients whose menses have not resumed as of the safety follow-up visit and for whom there is no explanation for the lack of resumption (eg, medical procedure or medications) will be contacted again by telephone 12 (± 2) weeks after the Safety Follow-up visit to determine if menses have resumed.

Complete data collected during the additional safety follow-up period will be summarized and reported in an addendum to the CSR.

4. GENERAL CONSIDERATIONS FOR DATA ANALYSES AND HANDLING OF MISSING DATA

4.1. Data Presentation Conventions

All statistical analyses will be conducted using SAS[®] Version 9.2 or higher.

All confidence intervals (CIs) will be reported as two-sided unless otherwise stated.

Where appropriate, variables will be summarized descriptively by study visit. For the categorical variables, the count and proportions of each possible value will be tabulated by treatment group. For continuous variables, the number of patients with non-missing values, mean, median, standard deviation (SD), minimum, and maximum values will be tabulated.

Unless otherwise specified, the following conventions will be applied to all analyses:

- Mean and median values will be formatted to one more decimal place than the measured value. Standard deviation values will be formatted to two more decimal places than the measured value. Minimum and maximum values will be presented to the same number of decimal places as the measured value. If the measured value is large (eg, > 100), fewer decimal places may be displayed.
- Percentages will be rounded to one decimal place;
- p-values will be rounded to four decimal places. p-values < 0.0001 will be presented as “< 0.0001” and p-values > 0.9999 will be presented as “> 0.9999”;
- 1 month = 30.4375 days. Month is calculated as (days/30.4375) rounded to one decimal place;
- 1 year = 365.25 days. Year is calculated as (days/365.25) rounded to one decimal place;
- Age will be calculated using the date of randomization. If only year of birth is collected, 1 July of the year of birth will be used to calculate age.
- 1 pound = 0.454 kg;
- 1 inch = 2.54 cm;
- Missing efficacy or safety data will not be imputed, unless otherwise specified;
- For laboratory results above or below sensitivity limits displayed as “<” or “>,” a quantification threshold, 0.000000001, will be subtracted or added, respectively, to the threshold to derive a numeric result for analyses;
- For MBL volume reported as below the limit of quantification (eg, MBL below Quantification Level < 5.0 mL or < 2.5 mL), 0.000000001 will be subtracted from the reported quantification threshold for the visit to derive a numeric result for analyses;
- For safety analyses, calculation of percentages will be calculated on the basis of the number of patients in the analysis population in each treatment group;
- For by-visit observed data analyses, calculation of percentages will be calculated on the basis of the number of patients with non-missing data as the denominator, unless otherwise specified;

- For other continuous endpoints, the summary statistics will include mean, SD, median, and range (minimum and maximum);
- For time-to-event endpoints, the summary statistics will include median time to event-free survival, 25th and 75th percentiles and number of patients at risk at specified time points;
- For categorical endpoints, the summary statistics will include counts and percentages;
- Confidence intervals, when presented, will generally be constructed at the 95% level. For binomial variables, exact methods will be employed, unless otherwise specified.

4.2. Analysis Populations

Four analysis populations are defined below. Number and percent of patients meeting the definition of each analysis population will be summarized by treatment group.

4.2.1. Modified Intent-to-Treat Population

Efficacy analyses will be performed using the modified Intent-to-Treat (mITT) population, unless otherwise specified. The mITT population consists of all patients randomized to treatment who have taken at least one dose of study treatment (relugolix/placebo or E2/NETA/placebo). Efficacy analyses will be performed by treatment group as randomized.

4.2.2. Per-Protocol Population

The Per-Protocol population consists of those patients in the mITT population who have no relevant major protocol deviations, defined as a subset of all major protocol deviations (see Section 5.2).

The Per-Protocol population will not be analyzed if this population comprises $> 95\%$ or $< 50\%$ of the mITT Population. This population will be used for supportive analysis of the primary efficacy endpoint. The Per-Protocol population will be identified prior to breaking the study blind.

4.2.3. Safety Population

The Safety population consists of all patients who were randomized and took at least one dose of study treatment. All safety analyses will be performed using the safety population, unless otherwise specified. Safety data will be analyzed by treatment group according to the actual treatment received (not the randomized treatment). Any patient who received at least one dose of relugolix during the randomized treatment period will be considered as a relugolix patient.

4.2.4. Retreatment Population

The Retreatment population consists of those patients in the mITT Population who started the retreatment. Selected efficacy and safety data will be analyzed using the retreatment population.

4.3. Definitions, Computation, and Convention

4.3.1. Definition of Date of First Dose and Date of Last Dose of Study Drug During the Randomized Treatment Period

The randomized treatment period is the period when a patient was on one of the randomized study drugs (relugolix + E2/NETA or placebo). The date of first dose of study drug is defined as the date when a patient receives the first dose of study drug for the randomized withdrawal study following randomization. The first dose of study drug for the randomized withdrawal study was to be self-administered the next morning following the Week 52/Baseline visit.

The date of the last dose of randomized study drug is defined as the date a patient receives the last dose of randomized study drug in this randomized withdrawal study, prior to re-treatment or on the Week 104 visit date. If the complete date of last dose of study drug is unknown, the last date the study drug was known to have been taken will be used.

4.3.2. Definition of Date of First Dose and Date of Last Dose of Retreatment Drug

The date of first dose of retreatment drug is defined as the date when a patient receives the first dose of retreatment drug (open-label relugolix + E2/NETA). When the return of heavy menstrual bleeding (defined as menstrual blood loss of ≥ 80 mL) was confirmed for a patient during the randomized treatment period, the patient was to be offered retreatment with open-label relugolix + E2/NETA with the onset of the next menses.

The date of the last dose of retreatment drug is defined as the date a patient receives the last dose of retreatment drug in this randomized withdrawal study, prior to or on the Week 104 visit date. If the complete date of last dose of retreatment drug is unknown, the last date the retreatment drug was known to have been taken will be used.

4.3.3. Study Day

Study day will be calculated with respect to the date of the first dose of randomized withdrawal study drug in this study (Study Day 1). For assessments conducted on or after the date of the first dose of randomized withdrawal study drug, study day will be calculated as:

$$(\text{Assessment date} - \text{date of first dose of randomized withdrawal study drug}) + 1$$

For assessments conducted before the date (and time) of the first dose of randomized withdrawal study drug, study day will be calculated as:

$$(\text{Assessment date} - \text{date of first dose of randomized withdrawal study drug})$$

For patients who do not receive any amount of randomized withdrawal study drug, study day will be calculated as above with respect to the date of randomization.

4.3.4. Definition of Treatment Duration During the Randomized Treatment Period

Treatment duration during the randomized treatment period is defined as the duration of time from the date of the first dose of study drug to the date of the last dose of study drug as follows:

$$(\text{Date of last dose of study drug} - \text{Date of first dose of study drug}) + 1$$

For patients without complete date of last dose of study drug, the last date study drug was known to have been taken will be used to calculate treatment duration. For patients who did not return for the Early Termination visits during the randomized treatment period, the time after their last visit will not be included in calculations of treatment duration.

4.3.5. Definition of Treatment Duration During the Retreatment Period

The retreatment period is the period when a patient was on the open-label retreatment drug. Treatment duration of retreatment drug is defined as the duration of time from the date of the first dose of retreatment drug to the date of the last dose of retreatment drug as follows:

$$(\text{Date of last dose of retreatment drug} - \text{Date of first dose of retreatment drug}) + 1$$

For patients without complete date of last dose of retreatment drug, the last date retreatment drug was known to have been taken will be used to calculate treatment duration. For patients who did not return for the Early Termination visits during the retreatment period, the time after their last visit will not be included in calculations of treatment duration.

The cumulative treatment period includes both the randomized treatment period and the retreatment period.

4.3.6. Definition of Baseline Value and Post-Baseline Value

Unless otherwise specified, Baseline values are defined as the last available measurement before the first administration (date and time) of study drug in the randomized withdrawal study. This is for randomized treatment period and for cumulative treatment period, which includes the randomized treatment and retreatment periods. A post-Baseline value is defined as a measurement taken after the first dose of study drug. Change from Baseline is defined as (post-Baseline value – Baseline value). Both date and time of study drug administration and measurement will be considered when calculating Baseline value. If the time is not available, then the date alone will be used. For patients who receive no study medication, the date of randomization will be used in place of the date of first dose in determining Baseline and post-Baseline values.

Baseline for the retreatment period is defined as the last available measurement before the first dose of retreatment drug unless otherwise specified. A post-retreatment-baseline value is defined as a measurement taken after the first administration of retreatment drug. Change from retreatment baseline is defined as (post-retreatment-baseline value – retreatment baseline value).

The BMD measurement taken at Week 52 of the extension study will be used as the Week 52/Baseline in the randomized withdrawal study, as long as it was within 30 days of the first dose date of the randomized withdrawal study drug. If there are multiple BMD measurements at Week 52 in the extension study, the one closest to the first dose date of the randomized withdrawal study drug will be used as Week 52/Baseline in the randomized withdrawal study.

For menstrual blood loss volume, the baseline definition will be specified in Section [7.3.2](#).

4.3.7. Visit Windows

Visit windows, which will be used to associate assessments with a scheduled visit, will be used only for summarizing data by visit. The windows for scheduled assessments are shown in

Table 2 (for monthly assessment, SF-36v2, PGA, WPAI-UF), **Table 3** (for BMD), **Table 4** (for UFS-QoL), and **Table 5** (for clinical laboratory tests and vital signs), respectively. For both efficacy and safety assessments, the study day will be used to determine the associated visit window.

The data collected in the paper diary related to bleeding and use of FPs will be assigned to visit windows as specified in **Table 6** and will be used to calculate the feminine product return rate (FPRR) as specified in Section 7.3.2.5.

If the results from more than one assessment are within a given visit window, the non-missing result from the assessment closest to the target date will be used except for FP collection, which is specified in Section 7.3.2.4. If two assessments are equally close to the target day, the earlier assessment will be used. For summaries of shift from Baseline in safety parameters, all values will be considered for these analyses.

Table 2: Visit Windows for Monthly Assessments

Visit (Long label)	Visit (Short label)	Start Day	Target Day	End Day
Week 56 (4 weeks after randomization) ^a	Week 56	1	29	43
Week 60 (8 weeks after randomization)	Week 60	44	57	71
Week 64 (12 weeks after randomization)	Week 64	72	85	99
Week 68 (16 weeks after randomization)	Week 68	100	113	127
Week 72 (20 weeks after randomization)	Week 72	128	141	155
Week 76 (24 weeks after randomization)	Week 76	156	169	183
Week 80 (28 weeks after randomization)	Week 80	184	197	211
Week 84 (32 weeks after randomization)	Week 84	212	225	239
Week 88 (36 weeks after randomization)	Week 88	240	253	267
Week 92 (40 weeks after randomization)	Week 92	268	281	295
Week 96 (44 weeks after randomization)	Week 96	296	309	323
Week 100 (48 weeks after randomization)	Week 100	324	337	351
Week 104 (52 weeks after randomization)	Week 104	352	365	Date of last dose + 14 days ^b

^a Start day of Week 56 for study day 1 includes only post-Baseline assessments that occurred after the first dose.

^b For SF-36v2, PGA, WPAI-UF, 14 days after date of last dose is used as the end day of Week 104.

Table 3: Visit Windows for Bone Mineral Density Assessments

Visit (Long label)	Visit (Short label)	Start Day	Target Day	End Day
Week 104 (52 weeks after randomization)	Week 104	281	365	449

Assessments will be excluded from analysis if they occur on or after the date of initiation of another investigational agent or hormonal therapy affecting the hypothalamic-pituitary-gonadal axis or surgical intervention for uterine fibroids. Assessments after date of last dose of study drug + 60 days will also be excluded from analysis.

Table 4: Visit Windows for UFS-QoL Assessments

Visit (Long label)	Visit (Short label)	Start Day	Target Day	End Day
Week 64 (12 weeks after randomization)	Week 64	64	85	106
Week 76 (24 weeks after randomization)	Week 76	148	169	196
Week 88 (36 weeks after randomization)	Week 88	197	253	308
Week 100 (48 weeks after randomization)	Week 100	309	337	351
Week 104 (52 weeks after randomization)	Week 104	352	365	421

Abbreviations: UFS-QoL = Uterine Fibroid Symptom and Health-Related Quality of Life.

Table 5: Visit Windows for Clinical Laboratory Tests and Vital Signs

Visit (Long label)	Visit (Short label)	Start Day	Target Day	End Day
Week 64 (12 weeks after randomization) ^a	Week 64	64	85	106
Week 76 (24 weeks after randomization)	Week 76	148	169	196
Week 104 (52 weeks after randomization)	Week 104	309	365	Date of last dose + 6 days
Safety Follow-Up ^b	Safety Follow-Up	Date of last dose + 7 days	Date of last dose + 30 days	Date of last dose + 60 days

^a This visit is only for clinical laboratory tests.

^b The safety follow-up visit window will be restricted to assessments prior to the date of initiation of another investigational agent or hormonal therapy affecting the hypothalamic-pituitary-gonadal axis or surgical intervention for uterine fibroids.

Table 6: Time Window for Feminine Product Collection

Visit (Long label)	Visit (Short label)	Feminine Product Collection Visit Date ^{a,b}	Time Window ^a
Week 56 (4 weeks after randomization) ^a	Week 56	X ₁	(Date of Study Day 1) – < X ₁
Week 60 (8 weeks after randomization)	Week 60	X ₂	(X ₁ +1) – ≤ X ₂
Week 64 (12 weeks after randomization)	Week 64	X ₃	(X ₂ +1) – ≤ X ₃
Week 68 (16 weeks after randomization)	Week 68	X ₄	(X ₃ +1) – ≤ X ₄
Week 72 (20 weeks after randomization)	Week 72	X ₅	(X ₄ +1) – ≤ X ₅
Week 76 (24 weeks after randomization)	Week 76	X ₆	(X ₅ +1) – ≤ X ₆
Week 80 (28 weeks after randomization)	Week 80	X ₇	(X ₆ +1) – ≤ X ₇
Week 84 (32 weeks after randomization)	Week 84	X ₈	(X ₇ +1) – ≤ X ₈
Week 88 (36 weeks after randomization)	Week 88	X ₉	(X ₈ +1) – ≤ X ₉
Week 92 (40 weeks after randomization)	Week 92	X ₁₀	(X ₉ +1) – ≤ X ₁₀
Week 96 (44 weeks after randomization)	Week 96	X ₁₁	(X ₁₀ +1) – ≤ X ₁₁
Week 100 (48 weeks after randomization)	Week 100	X ₁₂	(X ₁₁ +1) – ≤ X ₁₂
Week 104 (52 weeks after randomization) /EOT	Week 104/EOT	X _{Last} ^c	(Previous Feminine Product Returned Visit +1) – ≤ X _{Last}

^a If feminine products are collected at more than 1 visit within a given visit window (Table 2), the last feminine product collection date will be used to define the time window. If the patient missed the previous visit, a planned study visit date will be used to calculate the window.

^b In the absence of feminine product collection due to amenorrhea the visit date when amenorrhea was reported will be used.

^c Date of last non-missing feminine product collection within the interval from (previous visit end date + 1) to (last dose date + 7 days) (see Section 7.3.2).

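### SAP Table 5 caps only the Week 104 laboratory and vital-sign window at last dose + 6 days, so off-drug follow-up results can be reported as Week 64 or Week 76

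*SAP*

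**What the plan says.** SAP 4.3.7 uses visit windows only for summaries by visit, and states: "For both efficacy and safety assessments, the study day will be used to determine the associated visit window". If a window holds several results, the one nearest the target day is used; if two are equally near, the earlier one.

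Table 5 covers laboratory tests and vital signs:

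- Week 64, laboratory tests only (start, target and end day): "Week 64 64 85 106".
- Week 76: "Week 76 148 169 196".
- Week 104 starts on Day 309 and ends at "Date of last dose + 6 days".
- Safety Follow-Up starts at last dose + 7 days and ends at "Date of last dose + 60 days".

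The footnote to Safety Follow-Up removes results obtained after another agent or surgery. It does not say which window wins when a result fits two. For bone density, the note under Table 3 adds a limit of its own: "Assessments after date of last dose of study drug + 60 days will also be excluded from analysis".

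Under protocol 4.5, women taken off therapy have the Early Termination assessments and a follow-up visit about 30 days after the last dose. The Schedule of Activities (Table 1-1) gives that follow-up a window of -3 to +18 days and includes laboratory tests and vital signs. Its footnotes place the last dose in the clinic at the Week 104/Early Termination visit.

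**The concern.** The plan separates on-drug from follow-up results at Week 104: one window stops at last dose + 6 days and the other starts at + 7. For women who stop earlier, that boundary is missing. A follow-up sample taken a month after the last dose can land on a study day inside the Week 64 or Week 76 window and will then be read as an on-treatment result. The same sample also belongs to Safety Follow-Up. The sample taken on drug at Early Termination may meanwhile fall between windows and belong to no visit, or may lose to the later sample under the nearest-to-target rule. By-visit safety tables would then mix on-drug and off-drug values without showing it.

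**Working it through.** The plan gives no figure on this point to reproduce, so the check is day arithmetic on Table 5. The target days are consistent with 7 x weeks + 1: 7 x 12 + 1 = 85, 7 x 24 + 1 = 169, 7 x 52 + 1 = 365.

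**One record.** Last dose and Early Termination sample on Day 140, follow-up sample on Day 140 + 30 = 170.

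- Day 140 lies after 106 and before 148, so the on-drug sample has no visit.
- Day 170 lies in 148 to 196, so the off-drug sample is Week 76.
- Safety Follow-Up runs from 140 + 7 = 147 to 140 + 60 = 200, so the same sample is also Safety Follow-Up.

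**Which last-dose days are exposed.** Let L be the last-dose day, with the Early Termination sample on day L and follow-up on day L + 30.

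| | Week 64 | Week 76 |
|---|---|---|
| L + 30 inside the window | L = 34 to 76 (43 days) | L = 118 to 166 (49 days) |
| on-drug sample in no window | L = 34 to 63 (30 days) | L = 118 to 147 (30 days) |
| off-drug sample nearer the target, displaces the on-drug one | L = 64 to 69 (6 days) | L = 148 to 153 (6 days) |
| on-drug sample kept (nearer, or tied and earlier) | L = 70 to 76 (7 days) | L = 154 to 166 (13 days) |

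Example of displacement: with L = 150, the on-drug sample is 169 - 150 = 19 days from target and the Day 180 sample is 180 - 169 = 11 days from target, so the off-drug sample is used. With the protocol's full follow-up range (L + 27 to L + 48), the exposed last-dose days widen to 16 to 79 and 100 to 169.

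**How many women.** The 20% dropout rate is from SAP 2.2. Two assumptions are added: last-dose days are spread evenly over Days 1 to 364, and every dropout attends follow-up. For any fixed follow-up delay of 27 to 48 days, the chance of landing in a window is its length divided by 364.

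- Week 64: 0.20 x 43/364 = 2.4%
- Week 76: 0.20 x 49/364 = 2.7%
- Either: 0.20 x 92/364 = about 5%, and 0.20 x 92/364 x 360 = about 18 women, both arms together

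These are women with an off-drug result inside the window. With follow-up at + 30, the off-drug result is the one tabulated for 30 + 6 = 36 last-dose days at each visit: 0.20 x 36/364 = 2.0%, about 7 of 360 women per visit.

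**With the cap.** If both windows ended no later than last dose + 6 days, no result could be in them and in Safety Follow-Up, which starts at + 7.

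**The case against.** The case for leaving this alone is that little depends on it, and much of that case stands.

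- Windows serve by-visit summaries only. SAP 4.3.7 uses all values for shift summaries. The liver-elevation summaries (SAP 9.2) and vital-sign abnormality summaries (SAP 9.3.2) use post-baseline values, so an Early Termination result without a visit still counts there. The primary analysis uses event and censoring dates (SAP 7.3.1.2).
- The numbers are small. About 18 women cover two visits and two arms. Under 1:1 randomization about half were on placebo, for whom stopping is no pharmacological change. That leaves about 0.5 x 8.5 = 4 relugolix women at Week 64 and 0.5 x 9.7 = 5 at Week 76. Dropouts who skip follow-up lower this further.
- A result filed under two visit labels is not counted twice within one visit's summary.
- SAP 4.3.1 defines the randomized period as time on randomized drug, which an analyst might take as an implicit limit. But the by-visit laboratory summaries in SAP 9.2 are not restricted to that period, so the limit is not stated where it is needed.

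None of this supplies the missing cap or a precedence rule.

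**Conclusion.** The gap is real and follows from Table 5 as written, but its effect is small. Under even dropout of 20% and full follow-up attendance, an off-drug result falls in the Week 64 window for about 2.4% of women and in the Week 76 window for about 2.7%. It touches by-visit laboratory summaries at both visits and vital signs at Week 76.

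A reader might infer something stronger: that last dose in these tables means randomized drug, so women retreated after relapse lose their Week 104 results. With a last randomized dose on Day 120, for example, the Week 104 laboratory window would end on Day 126, before its Day 309 start, and a Day 365 scan would be later than Day 120 + 60 = 180. The documents do not support this as a rule:

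- SAP 4.3.1 says "The date of the last dose of randomized study drug is defined as the date a patient receives the last dose", with a qualifier that Tables 2, 3 and 5 lack. SAP 4.3.4 does use the bare term for randomized drug, but in a section confined to the randomized period.
- SAP 2.1, SAP 6 and protocol Table 5-1 count the open-label product as study drug.
- That reading would defeat the planned cumulative-period summaries and the Week 104 bone density summary for the whole safety population (SAP 9.3.3.1).
- It would not empty every questionnaire window in any case: the UFS-QoL Week 104 window is fixed at Days 352 to 421.
- One minus the planned responder rates (60% placebo, 40% relugolix) is not a retreatment rate. The documents give none, and women may decline retreatment.

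What remains is an unqualified term that deserves one clarifying sentence. If retreatment ends on Day 365 and last dose means any study drug, the limits become Day 371 (laboratory tests and vital signs), Day 379 (SF-36v2, PGA, WPAI-UF) and Day 425 (bone density), and no Day 365 result is lost.

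**What to change.** In SAP 4.3.7, Table 5, end the Week 64 and Week 76 windows at the earlier of the stated day (106 or 196) and last dose + 6 days, so that later results go only to Safety Follow-Up. For cumulative-period tables, last dose here means the last dose of any study drug, randomized or retreatment. In randomized-period tables, exclude results taken after the first retreatment dose. A cap at last randomized dose + 6 would not do this, because retreatment starts the day after the last randomized dose (protocol 6.2).

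As a clarification only, state that last dose in Tables 2, 3 and 5 means the last dose of any study drug for cumulative-period and bone density tables.

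The cost is SAP wording and a small programming change, with at most 2.4% fewer women contributing at Week 64 and 2.7% at Week 76. With follow-up at + 30 it is nearer 0.20 x 30/364 = 1.6% at each visit, since an on-drug result takes over where one is in the window. The cap does not give a visit to Early Termination results between windows, such as Day 140. Such a woman simply has no Week 76 value, which is accurate.
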